1.0 OBJECTIVES

In patients with CD30+ Lymphoproliferative Disorders (CD30+LYPDs)

1.1 Primary Objective

- To evaluate overall response rate of leflunomide treatment

1.2 Secondary Objectives

- To assess complete response rate and duration of response of leflunomide treatment
- To assess toxicities of leflunomide treatment
- To assess disease status by the CAILS (composite assessment of index lesion severity).

1.3 Exploratory Objectives

- To generate a preliminary RNA signature associated with response of CD30+LYPDs cells to leflunomide.

2.0 BACKGROUND

2.1 Introduction/Rationale for Development

The term “CD30+ T-cell lymphoproliferative disorders” (CD30+LYPDs) describes a group of diverse diseases of the skin.[1] Primary cutaneous CD30+ T cell lymphoproliferative disorders (pcCD30+ T cell LPDs) are the second most common type of cutaneous T cell lymphomas (CTCL), after mycosis fungoides (MF), accounting for 30% of all primary cutaneous lymphomas [2, 3]. CD30+LYPD includes primary cutaneous anaplastic large cell lymphoma (pCALCL) and lymphomatoid papulosis (LyP). Their diagnostic hallmark is CD30 expression by the atypical lymphocytes, in the same typical membranous and golgi pattern observed in systemic anaplastic large cell lymphoma (sALCL) [4]. The treatment and prognosis of cutaneous CD30+ T cell LPDs differ significantly from those of systemic lymphomas, emphasizing the importance of a clinical pathological correlation and thorough workup to ensure an accurate diagnosis [5].

For both LyP and pcALCL, treatments are determined by the extent of disease. In LyP, topical treatments such as corticosteroids and nitrogen mustard are not effective in changing the overall course of disease. Current therapies treat only current existing lesions and associated symptoms, such as pruritus [6, 7]. Patients with diffuse disease are treated with phototherapy or methotrexate [8]. Both therapies cannot be continued indefinitely due to the risk of long term side effects. Once these therapies are discontinued, lesions usually recur with the same intensity. In pcALCL, for single or localized lesions the main effective treatments are surgical excision or radiotherapy. For multifocal or recurrent pcALCL, systemic therapies are used such as methotrexate, bexarotene or Brentuximab Vedotin [9]. Treatment decision making is particularly challenging, given the toxic nature of available agents for a relatively indolent lymphoma.

2.2 Leflunomide

Leflunomide is a commercially available oral immunosuppressive agent that has been FDA approved since 1998 for the treatment of rheumatoid arthritis (RA) as a single agent or in combination with methotrexate. It has been used in over 300,000 patients worldwide for RA treatment. Leflunomide is generally well-tolerated and may be taken over a long period of time.

The in vitro and in vivo mechanisms of leflunomide are not completely defined. The primary clinical mechanism of action is inhibiting de novo pyrimidine synthesis by targeting dihydroorotate dehydrogenase (DHODH), and thus achieving anti-proliferative effect in B- and T-lymphocytes. A secondary mechanism of action is inhibition of cytokine and growth factor receptor associated tyrosine kinase activity [10].

Leflunomide (the pro-drug) is rapidly converted to its active primary metabolite teriflunomide (A77 1726), which mediates leflunomide's pharmacologic activity. Teriflunomide serum concentrations show wide inter-patient variability; in one study, the mean serum teriflunomide concentration in patients receiving 20 mg/ daily was 42 mg/l with a range from 3-150 mg/l and a standard deviation of 35 mg/l [11]. Of note, the serum concentration of this metabolite was shown to predict RA response [11].

The FDA approved dose in adults for the treatment of RA is a loading dose of 100 mg orally (PO) once daily for 3 days, followed by a maintenance dose of 10-20 mg PO once daily. Leflunomide has been used at up to 40 mg/day in patients with Wegner's granulomatosis with a safety profile similar to the 20mg/day dose used in RA [12, 13]. Doses up to 60 mg/day have been safely used for the treatment of allograft polyoma BK virus in renal allograft patients to achieve a targeted blood level of teriflunomide (A77 1726) of 50-100 micrograms/mL [14]; the targeted blood level was frequently achieved with a dose of 40mg/ day with no increase in toxicity reported [14].

In addition to studies that demonstrate the serum concentration of the metabolite may predict response, recent work demonstrates that polymorphisms in the gene encoding DHODH may be associated with leflunomide treatment outcome in RA patients[15, 16].

The long half-life of the metabolite (about 2 weeks) affects management of patients taking leflunomide. A loading dose of 100 mg for 3 days is used to facilitate rapid attainment of steady state levels of M1. Without a loading dose, it is estimated that attainment of steady state concentrations would require nearly two months of dosing [17]. To eliminate the metabolite, a drug elimination procedure using cholestyramine is recommended. Cholestyramine, a bile acid sequestrant, fixes the metabolite, preventing reabsorption and expediting drug elimination. Without the drug elimination procedure, it may take up to 2 years to reach non-detectable plasma levels after stopping treatment with leflunomide [17]

2.3 Preclinical Studies of Leflunomide as an antineoplastic agent

Leflunomide has been investigated for its anti-neoplastic potential in a variety of pre-clinical tumor models. The first reports of anti-tumor activity in mouse xenograft models of glioma indicate that inhibition of pyrimidine synthesis is not sufficient for anti-tumor activity and concomitant inhibition of tyrosine phosphorylation may also play a role[18]. In chronic lymphocytic leukemia (CLL), leflunomide has been shown to inhibit the cell cycle progression in primary leukemic cells in vitro [19]. Dietrich et al showed that teriflunomide (A77 1726) affects proliferation of CLL by blocking DHODH at very low concentration (3-5 μ g/ml) and by additionally inhibiting JAK/STAT pathway at intermediate concentrations (>10 μ g/ml)[20]. The metabolite is also effective in fludarabine-refractory cells [20]. In addition, pre-clinical anti-tumor activity of leflunomide has been reported for melanoma [21] and prostate cancer [22].

Recent pre-clinical studies of teriflunomide (A77 1726) have demonstrated significant antineoplastic activity in myeloma [23]. Teriflunomide inhibits cell growth and induces apoptosis in common myeloma cell lines at clinically achievable concentrations (50-200 μ mol/L) in a time- and dose-dependent manner. The stimulatory effect of conditioned medium of HS-5 bone marrow stromal cells on multiple myeloma cell growth is completely abrogated by teriflunomide. In addition, studies revealed additive effects when teriflunomide was combined with the genotoxic agents melphalan and doxorubicin and synergistic effects when combined with bortezomib and treosulfan[23]. Finally, the [name] laboratory has found leflunomide to be active in both glucocorticoid sensitive and resistant myeloma cell lines ([name], personal communication).

With respect to cutaneous lymphoma, the [name] laboratory has found the active metabolite teriflunomide to be effective at 48-72 hours in inducing apoptosis in mycosis fungoides, sezary syndrome, and CD30+LYPD cell lines. In particular, the apoptosis was achievable at the 50-200umol/L concentration.

2.4 Background for Correlative Studies

Leflunomide is rapidly converted to its active primary metabolite teriflunomide (A77 1726), which mediates leflunomide's pharmacologic activity. Previous population-based PK studies in patients with RA have demonstrated a high degree of intersubject variability in measured steady-state total (free + albumin-bound) teriflunomide serum concentrations, resulting in coefficients of variation in CL/F estimates of >50% [29, 30]. Teriflunomide is >99% bound to serum albumin and free drug concentrations have also been reported to be highly variable, with a median of 55.8 μ g/l and a range of 27.9-148.4 μ g/l [31]. Moreover, measured total and free teriflunomide levels have been shown to predict response and toxicity in RA patients, leading some investigators to suggest a role for therapeutic drug monitoring and dose optimization of leflunomide [16]. It has also been reported that genetic polymorphisms in CYP1A2 and CYP2C19, the hepatic enzymes responsible for leflunomide metabolism, and DHODH, a key enzyme in the *de novo* synthesis of pyrimidines and the main target of teriflunomide, can all influence the risk of leflunomide-associated toxicity in RA patients [32-34].

Transcriptomic diversity exists within the clonal tumor cells that comprise cutaneous lymphomas as noted by recent work in mycosis fungoides and Sézary Syndrome [24, 25]. This correlates with the clinical experience of many experts that monotherapy alone is unable to produce response rates higher than 30-40% or meaningful durations of response in these patients as well. In addition, it is not only the tumor heterogeneity but also the response to the tumor in the microenvironment in the form of T-cell exhaustion that contributes to a lack of higher response rates [26]. For these reasons, it is important to assess the heterogeneity of gene expression of tumor cells and the cells of the microenvironment that likely exists within CD30+LYPDs. Single-cell RNA analysis provides a view of all involved cellular components simultaneously and their individual gene expression states. Utilizing single cell mRNA sequencing will not only allow us to note the multiple mutations and the molecular signature of this group of diseases for the first time by assessing the baseline biopsies, but also will help us to explore the mechanism by which the leflunomide suppresses the growth of the CD30+LYPDs as noted in work conducted on CTCL lines by the [name] group. In addition, this will contribute to determining what future combination therapies can be utilized for better clinical and durable response as well as for tailoring patient-specific treatment.

The parallel assessment of immunohistochemistry will allow us to correlate the new single cell data with what is seen/noted pathologically. Tumor cells in CD30+LYPD will be characterized utilizing a standard immunohistochemistry panel which includes CD3, CD4, CD8, CD30, BF1, Gamma, TRAF1, MUM1, perforin, granzyme, TIA-1 [27]. Current work in this area has noted that the predominant cells in the tumor microenvironment of CD30+LYPDs include a large percentage of CD163+ macrophages (M2) (44.7% in LyP vs. 35% in pcALCL). However, there are a number of tumor infiltrating CD8+ lymphocytes, FOXP3+ T-regulatory cells (Tregs) and only a few programmed cell death (PD1) lymphocytes [28]. We would like to examine the effect leflunomide has on the changing microenvironment as well.

2.5 Overview and Rationale of Study Design

Teriflunomide, the active metabolite of leflunomide, is approved for treatment of multiple sclerosis [15]. The "on target" effect of leflunomide and teriflunomide, which occurs at low doses, is mediated through inhibition of the cellular dihydroorotate dehydrogenase (DHODH) enzyme [16]. DHODH is required for *de novo* pyrimidine synthesis (but not for pyrimidine synthesis mediated by the salvage pathway), and "on target" effects of the leflunomide/teriflunomide are reversed *in vitro* by supplementing the media with uridine, which restores *de novo* pyrimidine synthesis. Lymphocytes are particularly dependent upon *de novo* pyrimidine synthesis for their proliferation [17], and the major "on target" immunosuppressive effect of leflunomide/teriflunomide is thought to be due to decreased T cell proliferation. In addition to decreasing the amount of pyrimidine-based nucleotides available for DNA/RNA synthesis, drugs that inhibit DHODH activity globally decrease the level of O-linked GlcNAcylate-modified proteins through an "on-target" effect [18]. Diffuse large B-cell lymphoma (DLBCL) cell lines and primary DLBCL tumor cells have higher levels of nuclear O-GlcNAcylate-modified proteins than do normal B-cells, and the levels of these proteins correlate with DLBCL cell growth and survival [19]. With respect to cutaneous lymphoma the [name] laboratory has found the active metabolite teriflunomide to be effective at 48-72 hours

in inducing apoptosis in mycosis fungoides, Sézary cell, and CD30+LYPD cell lines. In particular, the apoptosis was achievable at the 50-200umol/L concentration.

These pre-clinical data, and the relatively low toxicity profile seen with prolonged administration in the rheumatoid arthritis population as well as the multiple myeloma population, in total provide evidence to support the investigation of leflunomide as an anti-CD30+ agent.

While the standard dose of leflunomide (20mg daily), following a loading dose of 100mg daily for 3 days, is FDA approved for continuous treatment of rheumatoid arthritis, leflunomide has been administered without an increase in the type, frequency or severity of adverse events at doses up to 40 mg/day in patients with Wegner's granulomatosis, and up to 60mg/day in a subset of patients with polyoma BK neuropathy to achieve targeted therapeutic levels [12, 13].

Because the current dosing guideline for patients with rheumatoid arthritis do not to exceed 20 mg daily maintenance doses [17], the 20mg/day dose is selected as the safe starting dose. In addition, in personal communications, [name] has used leflunomide at doses of 10-20mg daily for 6 weeks in patients who have failed methotrexate with report of minimal side effects.

Patients will be treated in planned 28-day treatment cycles. Patients may continue to receive cycles of treatment on study until disease progression or unacceptable toxicity, or other criteria for removal from study treatment are satisfied. While on active treatment patients will undergo monthly evaluation for response by mSWAT and the CAILS (composite assessment of index lesion severity) [29, 30]. Following the decision to end leflunomide treatment, all patients will undergo 11 days of treatment with cholestyramine, which fixes the metabolite, preventing re-absorption and effectively lowering drug levels. Cholestyramine has been shown to decrease plasma levels of teriflunomide (A77 1726) in healthy volunteers by approximately 40% in 24 hours and by 49-65% in 48 hours [17].

In addition, molecular correlates and *ex vivo* responses will be evaluated using skin specimens, which will be collected from patients before treatment, after one cycle, four cycles of leflunomide treatment, end of therapy (if lesions are still present), and at disease progression. Molecular correlate analysis of leflunomide response will include single cell RNA sequencing. Specimens derived from before and after leflunomide treatment (after 1 month and at progression or complete response, if possible) will be analyzed, as well as pre-treatment specimens exposed to teriflunomide *ex vivo*.

3.0 ELIGIBILITY CRITERIA

Patient MRN (COH Only)

Patient Initials (F, M, L):

Participants must meet all of the following criteria on screening examination to be eligible to participate in the study:

3.1 Inclusion Criteria

Informed Consent

- ___ 1. Documented informed consent of the participant and/or legally authorized representative.
 - Assent, when appropriate, will be obtained per institutional guidelines

Age Criteria, Performance status

- ___ 2. Age: ≥ 18 years
- ___ 3. Patients must have a life expectancy of > 3 months
- ___ 4. ECOG ≤ 2

Nature of Illness and Illness Related Criteria

- ___ 5. Patients must have a diagnosis of cutaneous CD30+LYPD
- ___ 6. Patients must be relapsed or are refractory to at least 1 prior line of therapy
- ___ 7. At least 2 weeks from prior therapy to time of start of treatment. Prior therapy includes steroids (except prednisone or equivalent – up to 10 mg/day is allowed).

Clinical Laboratory and Organ Function Criteria (To be performed within 21 days prior to Day 1 of protocol therapy unless otherwise stated [see Section 10.0])

 ___ 8. ANC $\geq 1000/\text{mm}^3$ NOTE: Growth factor is not permitted within 14 days of ANC assessment unless cytopenia is secondary to disease involvement. 	ANC: 	Date:

 ___ 9. Platelets $\geq 50,000/\text{mm}^3$ NOTE: Platelet transfusions are not permitted within 14 days of platelet assessment unless cytopenia is secondary to disease involvement. 	Plts: 	Date:

 ___ 10. ___ 10. Total bilirubin $\leq 1.5 \times \text{ULN}$ (unless has Gilbert's disease) 	ULN: Bil: 	Date:

 ___ 11. AST $\leq 2.0 \times \text{ULN}$ 	ULN: AST: 	Date:

 ___ 12. ALT $\leq 2.0 \times \text{ULN}$ 	ULN: ALT: 	Date:

 ___ 13. Creatinine clearance of $\geq 30 \text{ mL/min}$ per 24 hour urine test or the Cockcroft-Gault formula or $\text{CrCl (mL/min)} = \frac{(140-\text{age}) \times \text{actual body weight (kg)}}{72 \times \text{serum creatinine (mg/dL)}} \times 0.85 \text{ for females}$ 
Or
 $\text{CrCl (mL/min)} = \frac{(140-\text{age}) \times \text{actual body weight (kg)}}{0.8136 \times \text{serum creatinine (umol/L)}} \times 0.85 \text{ for females}$ 	Serum Cr: Cr Clearance: 	Date:


___ 14. Seronegative for HIV Ag/Ab combo, HCV*, active HBV (Surface Antigen Negative) *If positive, Hepatitis C RNA quantitation must be performed.
 
___ 15. Meets other institutional and federal requirements for infectious disease titer requirements Note Infectious disease testing to be performed within 28 days prior to Day 1 of protocol therapy.
 
___ 16. Negative for tuberculosis antigen (e.g. T-Spot test).
 
___ 17. Women of childbearing potential (WOCBP): negative urine or serum pregnancy test If the urine test is positive or cannot be confirmed as negative, a serum pregnancy test will be required
	
HIV: HCV: HBV: Syphilis:
 
Urine: Serum: Date:
	
Date:

Contraception

___ 18. Agreement by females **and** males of childbearing potential* to use an effective method of birth control (hormonal or barrier method of birth control or abstinence) or abstain from heterosexual activity for the course of the study through at least three months after the last dose of protocol therapy. The effects of study treatment on a developing fetus have the potential for teratogenic or abortifacient effects. Should a woman become pregnant or suspect that she is pregnant while participating on the trial, she should inform her treating physician immediately.

* Childbearing potential defined as not being surgically sterilized (men and women) or have not been free from menses for > 2 years (women only).

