Diarrhea Grade 4 (≥10 stools/day > baseline)	
At 20 mg:
 
Hold study agent and provide optimal anti-diarrheal therapy.
 
If does not resolve to Grade 3 within 48 hours, permanently discontinue study agent.
 
If resolves to Grade 3 within 48 hours, then:
 
First Occurrence:
 
 Hold until resolution to ≤ grade 1. If resolved in ≤ 7 days, resume at pre-hold dose. If resolved in 8-14 days, resume study agent at 10 mg. If not resolved within 14 days, permanently discontinue study agent. 
Recurrence:
 
 Hold until resolution to ≤ grade 1. If resolved in ≤ 14 days, resume study agent at 10 mg. If not resolved within 14 days, permanently discontinue study agent. 
At 10 mg: Permanently discontinue study agent.

Vomiting or Nausea Grade 1	Maintain study agent.
Vomiting or Nausea Grade 2	Maintain study agent.
Vomiting or Nausea Grade 3	
At 20 mg:
 
Hold study agent and provide optimal supportive care/therapy.
 
First Occurrence:
 
 If resolves to ≤ grade 1 in ≤ 7 days, resume at pre-hold dose. If resolves to ≤ grade 1 in 8-14 days, resume study agent at 10 mg. If does not resolve within 14 days, permanently discontinue study agent. 
Recurrence:
 
 If resolves to ≤ grade 1 in ≤ 14 days, resume at 10 mg. If does not resolve within 14 days, permanently discontinue study agent. 
At 10 mg: Permanently discontinue study agent.

Vomiting Grade 4	
At 20 mg:
 
Hold study agent and provide optimal supportive care/therapy.
 
If does not resolve to Grade 3 within 48 hours, permanently discontinue study agent.
 
If resolves to Grade 3 within 48 hours, then:
 
First Occurrence:
 
 Hold until resolution to ≤ grade 1. If resolved in ≤ 7 days, resume at pre-hold dose. If resolved in 8-14 days, resume study agent at 10 mg. If not resolved within 14 days, permanently discontinue study agent. 
Recurrence:
 
 Hold until resolution to ≤ grade 1. If resolved in ≤ 14 days, resume study agent at 10 mg. If not resolved within 14 days, permanently discontinue study agent. 
At 10 mg: Permanently discontinue study agent.

Hepatic investigations	
ALT (SGPT) or AST (SGOT) ≤ 3.0 x ULN or TBili ≤ 1.5 x ULN	Maintain study agent.

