ALT (SGPT) or AST (SGOT) >3.0 - 5.0 x ULN or TBili >1.5 - ≥ 3.0 x ULN	
First Occurrence:
 
Hold until resolution to < 3.0 x ULN for ALT or AST or < 1.5 for TBili. Resume at pre-hold dose if resolved within 14 days. If does not resolve within 14 days, permanently discontinue study agent.
 
Recurrence:
 
Hold until resolution to < 3.0 x ULN for ALT or AST or <1.5 for TBili. Resume at 10 mg if resolved within 14 days. If does not resolve within 14 days, permanently discontinue study agent.

ALT (SGPT) or AST (SGOT) > 5.0 x ULN or TBili > 3.0 x ULN	Permanently discontinue study agent.
Electrolyte/metabolic toxicity	
Electrolyte/metabolic Grade 3	
Provide support care. Maintain study agent per investigator discretion.
 
If alteration persists despite aggressive replacement therapy, then dose reduce or permanently discontinue (per investigator discretion with PI consultation).

Electrolyte/metabolic Grade 4	
Provide support care. Maintain study agent per investigator discretion.
 
If resolves to Grade 1 or baseline within 48: for first event, maintain at pre-hold dose; for recurrent event, dose reduce or permanently discontinue (per investigator discretion with PI consultation).
 
If does not resolve to Grade 1 or baseline within 48 hours, permanently discontinue study agent.

Other unspecified Non-Hem toxicities considered related to leflunomide	
Grade 1	Maintain study agent.
Grade 2	Maintain study agent.
Grade 3	
First Occurrence:
 
Hold until resolution to ≤ Grade 2. Resume at pre-hold dose if resolved within 7 days. If does not resolve within 7 days, permanently discontinue study agent.
 
Recurrence:
 
Hold until resolution to ≤ Grade 1. Resume at 10 mg if resolved within 14 days. If does not resolve within 14 days, permanently discontinue study agent.

Grade 4	Permanently discontinue study agent.
Other unspecified Non-Hem Toxicities considered UNRELATED to study agent	
Other unspecified events of any grade considered unlikely to be related or not related to study agents.	Maintain treatment with study agents. Interruption of study agent or dose de-escalation is permitted if the investigator consults with the Principal Investigator to determine that this is in the best interest of the participant.

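### The bilirubin hold row in Table 7.1.1 makes no allowance for a Gilbert's patient whom item 10 admits with a baseline already above 1.5 x ULN

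*Combined protocol and SAP*

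**What the plan says.** **Entry.** Section 3.1, item 10 requires total bilirubin of at most 1.5 x ULN "unless has Gilbert's disease". It gives no upper limit for a patient who has the condition. Gilbert's disease is mentioned nowhere else in the document. Registration (Section 4.2.3) runs from the Section 3.0 checklist, which carries the waiver.

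**On treatment.** The hepatic part of Table 7.1.1 (Section 7.1.2) has three rows:

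- Maintain: "ALT (SGPT) or AST (SGOT) ≤ 3.0 x ULN or TBili ≤ 1.5 x ULN".
- Hold: for bilirubin, "TBili >1.5 - ≥ 3.0 x ULN" (the second sign is evidently a misprint for an upper bound). The action is "Hold until resolution to < 3.0 x ULN for ALT or AST or < 1.5 for TBili". A first event resumes at the previous dose; for a recurrence, "Resume at 10 mg if resolved within 14 days". In both cases, "If does not resolve within 14 days, permanently discontinue study agent".
- Stop permanently: "ALT (SGPT) or AST (SGOT) > 5.0 x ULN or TBili > 3.0 x ULN".

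None of these rows refers to baseline or to relatedness. Section 7.1.1c does define a baseline value, and the Grade 4 electrolyte row uses one. The table's allowance for unrelated events is confined to "Other unspecified events of any grade considered unlikely to be related or not related to study agents". Bilirubin has its own rows, so that allowance does not reach it.

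**The concern.** The waiver deliberately admits patients whose usual bilirubin may lie above 1.5 x ULN. The hold row then treats the same value as a reason to interrupt the drug and asks for a fall below 1.5 that a patient at a stable baseline would not show. A patient the protocol meant to treat could lose treatment within about a month because of a pre-treatment value, and would then go through the 11-day cholestyramine procedure of Section 5.5. If staff see the mismatch and set the row aside, they have no written rule for what rise above the patient's own level should lead to a hold, or what level allows the drug to resume. Section 6.1 lists hepatitis and hepatic failure for leflunomide, so that rule is worth having. What is at stake is the handling of an individual patient, not the trial's inference.

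**Working it through.** **1. Action by bilirubin level.** Take a patient with ALT and AST at 1 x ULN and read the misprinted band as above 1.5 to 3.0. The rows join the analytes with 'or', so two readings are shown.

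| Bilirubin (x ULN) | Each analyte on its own, worst governs | Literal 'or' |
|---|---|---|
| 1.4 | maintain | maintain |
| 1.6, 2.0, 2.9 | hold; stop at 14 days if unchanged | meets maintain and hold rows |
| 3.1 | stop at once | meets maintain and stop rows |

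The literal reading puts one patient in two rows with different actions, so it settles nothing. The first reading is the ordinary one for a toxicity table.

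**2. Timing on the ordinary reading.** Inputs: 13 cycles of 28 days (Section 5.1); first on-treatment chemistry on Day 14 +/- 3 (Section 10.0, footnote c); 14-day limit (hold row). Assume that the result is acted on the same day and that day's dose was taken.

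- Planned dosing days: 13 x 28 = 364.
- Last dose: 14 - 3 = Day 11 to 14 + 3 = Day 17.
- Permanent stop after the hold: 11 + 14 = Day 25 to 17 + 14 = Day 31. Above 3.0 x ULN there is no hold, so the stop falls on Day 11 to 17.
- Share of planned dosing days: 11/364 = 3.0% to 17/364 = 4.7%.
- Share of planned milligrams, with three loading doses of 100 mg and 20 mg daily after that: (300 + 8 x 20)/(300 + 361 x 20) = 460/7,520 = 6.1% to (300 + 14 x 20)/7,520 = 580/7,520 = 7.7%.

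Exposure lasts longer than dosing, because the metabolite's half-life is about 2 weeks (Section 2.2). A patient whose bilirubin falls below 1.5 x ULN during the hold may resume, at 10 mg after a recurrence.

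**3. If the rows are set aside for a stable pre-treatment value.** Take a baseline of 1.8 x ULN. The hold trigger (above 1.5) is met before any drug effect, and the resume level (below 1.5) lies under the patient's usual value, so neither is usable. A drug-related rise to 3.2 still meets the stop row. That row works for any baseline of 3.0 or less and fails only for a baseline above 3.0, which item 10 does not rule out.

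**4. How many patients.** The document gives no prevalence. If a share p of patients has Gilbert's disease and entry bilirubin above 1.5 x ULN, the chance of at least one among n is 1 - (1 - p)^n. For assumed p of 2%, 5% and 10% this is 22%, 46% and 72% with n = 12, and 25%, 51% and 77% with n = 14. These shares are illustrative. An actual stop also needs bilirubin to stay at 1.5 x ULN or more through the hold (or to exceed 3.0), and staff to apply the rows as printed.

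**5. Response rate.** A stopped patient with one post-baseline assessment remains evaluable and is not replaced (Section 12.3). The ceiling is 1/12 = 8.3 percentage points per patient, reached only if that patient would otherwise have responded later.

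**The case against.** The strongest reply is that the table does not oblige anyone to stop this patient. Its first column is headed as adverse events. Section 7.1.2 presents it as dealing with toxicities and says it is to be used together with Section 7.1.1, where item d ties the 14-day stop to toxicities related to the study agent. Section 5.6 likewise speaks of intolerance caused by toxicity. A stable pre-treatment bilirubin is not a new event. A purely mechanical reading would even trip on the Cycle 1 Day 1 chemistry, before the first dose, which cannot be intended. This stands as far as it goes: a reader might infer that the protocol mandates a stop, and the text does not support so firm a conclusion. It leaves the rule ambiguous, however, because the hepatic rows are triggered by the laboratory value and carry their own 14-day stop with no relatedness condition.

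A reader might also infer that, once the rows are set aside, the patient has no bilirubin safeguard. That is not so. The stop row above 3.0 x ULN still works for a baseline of 3.0 or less, the ALT and AST limits apply unchanged, and Sections 5.6 and 5.8 allow removal on the investigator's judgement. What is lost is a usable hold trigger and resume level.

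The synopsis gives a bilirubin limit without the waiver and lists pre-existing liver disease as an exclusion that Section 3.2 does not carry. Little should be built on this: the list is headed as abbreviated, and whether Gilbert's disease counts as liver disease is not stated. Exclusion 11 also lets an investigator refuse entry on safety grounds. These points narrow the route by which such a patient enters but do not close it.

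**Conclusion.** The concern holds as a minor conflict between two rules. On the ordinary reading, the hold row gives the wrong action for a patient whom item 10 expressly admits; on the lenient reading, its hold and resume thresholds do not fit that patient. The consequence is confined to the treatment of any such patient. The number is unknown and may be zero. The effect on the overall response rate is negligible in a descriptive pilot whose sample size rests on feasibility: the 8.3-point ceiling should not be read as an expected bias. The timing rests on the Day 14 window, same-day action and an unchanged bilirubin. Confidence is moderate, because the outcome depends on how staff would read the table.

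**What to change.** Preferred:

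- In item 10, cap the waiver at total bilirubin of 3.0 x ULN, so that the stop row is meaningful for everyone enrolled.
- In Table 7.1.1, for Gilbert's patients with baseline above 1.5 x ULN: maintain at the Section 7.1.1c baseline; hold on a rise above baseline by a margin that the sponsor's clinicians set; resume on return to baseline instead of below 1.5; keep the stop above 3.0 x ULN and the ALT and AST limits as they are.

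The clinicians should check that the margin leaves room below the stop row: at a baseline of 1.8 there is 3.0 - 1.8 = 1.2 x ULN, at 2.9 only 0.1. They may therefore prefer a lower cap.

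The cost is one limit and one table row. No extra tests are needed, because total bilirubin is already in the chemistry panel.

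Alternative: delete the waiver from item 10. This is a single deletion; the price is an occasional lost candidate in a rare disease.
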